## **10.0 Inclusion and Exclusion Criteria\***

### **10.1 Describe how individuals will be screened for eligibility.**

In-person: Individuals will be screened for eligibility by a member of our research team on recruitment days at various Juvenile Traffic Courts in Ohio.

Virtual: Individuals who are interested can scan a QR code from a study flyer that will be placed in the Juvenile Traffic Courts. The QR code will lead the teen and parent to an eligibility form that is on REDCap.

### **10.2 Describe the criteria that define who will be included or excluded in your final study sample.**

The study population will include 240 parent-teen dyads (80 per group), each of which includes a teen (16 or 17 years) with intermediate license who committed a moving violation during the

## PROTOCOL TITLE: Intervention to Improve Driving Practices Among High-Risk Teen Drivers

recruitment period (study months 7 to 42) and the parent who is most involved with the teen's driving. Participants will be selected without regard to sex, race/ethnicity, or socioeconomic status.

### **Inclusion criteria**

- Age 16-17 years at time of violation/traffic warning;
- Convicted of a moving violation or received a traffic warning;
- Possess a valid intermediate driver's license issued by the state of Ohio, with proof of car insurance;
- Access to a vehicle with an On-board Diagnostics II system port (i.e., cars made after 1996) in which he/she is the primary driver;
- Smartphone with Bluetooth capabilities;
- At least one legal guardian.

### **Exclusion criteria**

- Unable to drive due to injury, license suspension, or car damage;
- Vehicle already has an in-vehicle driving feedback system installed;
- Extremely low average weekly drive time (e.g. <1 hour per week);
- Currently enrolled in another driving-related study;
- Ward of the State;
- Non-English speaking parent.

### **10.3 Indicate specifically whether you will include or exclude each of the following special populations: (You may not include members of the above populations as subjects in your research unless you indicate this in your inclusion criteria.)**

- 10.3.1 Adults unable to consent (exclude)
- 10.3.2 Individuals who are not yet adults (infants, children, teenagers) (include)
- 10.3.3 Pregnant women (exclude)
- 10.3.4 Prisoners (exclude)

### **11.0 Vulnerable Populations\***

#### **11.1 If the research involves individuals who are vulnerable to coercion or undue influence, describe additional safeguards included to protect their rights and welfare.**

Participating in the study will not affect a participant's court hearing. Clinical services will not be provided as part of this study. To ensure individuals are not coerced to participate in the study by the court, all meetings between participants and research staff, including the initial meeting at the courthouse, will occur only after the teens' court hearing and after they have received the judge's final decision. No court officials will be involved in the recruitment process or implementation of the study protocols and intervention. Additionally, the judge will be blinded from the identity of any teens and parents who choose to participate in the study.

### **12.0 Local Number of Subjects**

#### **12.1 Indicate the total number of subjects to be accrued locally.**

240 parent-teen dyads

### **13.0 Recruitment Methods**

#### **13.1 Describe when, where, and how potential subjects will be recruited.**

In-person: We will house two research staff members at the courthouse each week (varying by day of week) from 8:30 a.m. to 11:00 a.m., while the juvenile traffic court is in session. On days of recruitment, the teens and their parents will be approached by our on-site research staff members following their scheduled court hearing. The research team member will clearly indicate to the teen and their parent that they are not part of the judicial system. Staff will distribute the study information sheet/flyer to the teen and parent, emphasizing that participation in this study will not impact the court ruling. Interested dyads will then meet our on-site research staff to learn study

## PROTOCOL TITLE: Intervention to Improve Driving Practices Among High-Risk Teen Drivers

details, ask questions, be screened for eligibility, and sign consent/assent documents either on-site in a private room or later at a time that is convenient to them. Only dyads with both parent and teen consent/assent will be enrolled. Enrolled participating dyads will then complete a baseline assessment before being randomly assigned into one of three study groups. The judge, who will not be engaged in study recruitment, will be blinded from the identity of dyads who choose to participate in the study and no other court staff will be involved with recruitment for this study. Refusal to participate in this study will have no penalty or loss of benefits to which teen drivers are otherwise entitled and will not affect the outcome of their court hearing in any way.

Virtual: We will have study flyers posted around the waiting room at the Juvenile Traffic Courts. We will share the testimonial video with the courts and other community/school events. Teens and parents who are interested will have the ability to scan the QR code on the flyer which will lead them to our eligibility screening form on REDCap. If the teens and parents are eligible, they will be contacted by our research team to schedule a meeting to virtually sign the consent/assent form and be enrolled in the study. If we contact the potential participant 3 or more times then we will assume they are not interested. We will send them a final email included in the script document. Only dyads with both teen and parent consent/assent will be enrolled. The judge, who will not be engaged in study recruitment, will be blinded from the identity of the dyads who choose to participate in the study. Refusal to participate in this study will have no penalty or loss of benefits to which teen drivers are otherwise entitled and will not affect the outcome of their court hearing in any way.

### **13.2 Describe the source of subjects.**

Our subjects will be drawn from various Juvenile Traffic Courts in Ohio. We will recruit teen drivers aged 16-17 who present to court for their mandated court hearing following a traffic violation.

### **13.3 Describe the methods that will be used to identify potential subjects.**

In-person: Interested dyads will meet our on-site research staff to learn study details, ask questions, and will be screened for eligibility. Researchers will also recruit interested dyads at community/school events, such as Carteens.

Virtual: Interested dyads who are interested will have the ability to scan a QR code that will lead them to our eligibility screening form through REDCap. We will share the testimonial video with courts, collaborators, and other community/school events (e.g., Carteens). Participants will be recruited virtually through multiple online avenues including social media, research databases (e.g., Studysearch, ResearchMatch), and other relevant listservs (e.g. Peachjar).

### **13.4 Describe materials that will be used to recruit subjects. (Attach copies of these documents with the application).**

In-person: Information sheets will be used to describe the study to potential participants.

Virtual: Study flyers designed by NCH will be used to describe the study to potential participants. These flyers will be posted in various community locations such as recreational center, grocery stores, and schools. Approval from the location will be obtained prior to posting the flyer.

Testimonial video designed by NCH will be used to share the experiences of parents and teens that completed the study with potential participants.

### **13.5 Describe the amount and timing of any payments to subjects.**

The participating dyad, regardless of group assignment, will receive compensation up to \$240 for teen (\$30 per month x 6, plus \$20 per survey x 3), and \$180 for parent (\$20 per month x 6, plus \$20 per survey x 3). Parents in who receive the communication training will receive an additional \$20 for completing a survey after the individualized communication training.

## **14.0 Withdrawal of Subjects\***

### **14.1 Describe anticipated circumstances under which subjects will be withdrawn from the research without their consent.**

## PROTOCOL TITLE: Intervention to Improve Driving Practices Among High-Risk Teen Drivers

There are no anticipated circumstances under which subjects will be withdrawn from the research without their consent.

### 14.2 Describe any procedures for orderly termination.

There are no procedures for orderly termination.

### 14.3 Describe procedures that will be followed when subjects withdraw from the research, including partial withdrawal from procedures with continued data collection.

There are no clinical procedures that need to occur if subjects withdraw from the research. If a subject chooses to withdraw from the study, a member of our research team will arrange a time with the subjects to collect the study devices.

## 15.0 Risks to Subjects\*

### 15.1 List the reasonably foreseeable risks, discomforts, hazards, or inconveniences to the subjects related the subjects' participation in the research. Include as may be useful for the IRB's consideration, a description of the probability, magnitude, duration, and reversibility of the risks. Consider physical, psychological, social, legal, and economic risks.

The potential risks posed to the study participants will be minimal. We acknowledge that there is the potential for emotional stress for the teen participant during the study. However, the stress related to the study is no more than that of day-to-day life. Participants will not be required to answer any questions that they feel uncomfortable answering and will be ensured that their participation in this study is completely voluntary and they are permitted to leave the study at any time. Participants will also be ensured that refusal to participate in this study will have no penalty or loss of benefits to which teen drivers are otherwise entitled. The notifications provided by the study devices (direct feedback beeps and push notifications on app) will be different from what the participants may be accustomed to, however the risk posed by these in-vehicle devices while the subject is driving will be minimal. All information provided by the participant will be kept confidential, and will not be disclosed to family, friends, law enforcement, or the juvenile traffic court.

## 16.0 Potential Benefits to Subjects\*

### 16.1 Describe the potential benefits that individual subjects may experience from taking part in the research. Include as may be useful for the IRB's consideration, the probability, magnitude, and duration of the potential benefits.

The benefit(s) of the study include teens driving more safely after receiving real-time driving feedback and seeing their driving data and parents learning communication strategies specific to teen driving safety to help motivate their teens to adopt safe driving practices.

## 17.0 Data Management\* and Confidentiality

### 17.1 Describe the data analysis plan, including any statistical procedures or power analysis.

Our sample size was determined for powering **Aim 1**, based on the primary outcome, the rate of risky driving events using data from our published work, pilot study data, and design parameters. The risky driving events are count data, which will be modeled by Quasi-Poisson distribution with an over-dispersion factor of 25 (based on our pilot study,  $\frac{Var}{Mean} = \frac{32.7^2}{43} = 24.9$ ) for the ordinary Poisson variability. We assume the three groups have the same over-dispersion factor for the Quasi-Poisson distributed data. With these design parameters and 3 groups of an equal sample size of 74, this study will have 0.80 or higher power to detect that Group 2 will have fewer risky driving events than Group 1, and Group 3 will have fewer risky driving events than Group 2, using a one-way ANOVA and adjusting for two-sided multiple comparisons. Based on these sample sizes and less than 10% loss to follow-up, we will recruit and enroll 80 dyads per group (a total of 240).

For the primary outcome of risky driving events (hard braking, sudden acceleration, speeding), the overall rate and rate for each type of event per 1,000 miles driven will be calculated for each teen at

## PROTOCOL TITLE: Intervention to Improve Driving Practices Among High-Risk Teen Drivers

6-month follow-up. To compare the differences among the 3 groups, one-way ANOVAs will be used. To model the effects of the intervention on the rates of risky driving events per 1,000 miles driven, a Quasi-Poisson analysis for over-dispersed count data will be conducted, where 2 dummy variables indicating Groups 2 and 3 will be created as covariates to determine risk ratios of risky driving events among the 3 groups, adjusting for the other potential covariates.

For the primary outcome of unsafe driving behaviors (speeding, distracted driving, no seatbelt use), to model the effects of the intervention on the proportion of unsafe behaviors per 1,000 miles driven, Quasi-Poisson analysis for over-dispersed count data will be implemented, where two dummy variables indicating Groups 2 and 3 will be created as covariates to determine the risk ratios of unsafe driving behavior among the 3 groups, adjusting for the potential covariates described above. In addition, a secondary analysis of correlation coefficients will be conducted to ascertain if and how the risky driving events and unsafe driving behaviors are correlated and whether the correlations are different between the study groups. The potential covariates will be adjusted.

For the secondary outcome of frequency and quality of parent-teen communication about driving safety, to model the effects of the intervention on differences in frequency and quality of parent-teen communication among the 3 groups, an Analysis of covariance (ANCOVA) will be used for each outcome, adjusting for the potential covariates. In addition, the following secondary analyses will be performed: 1) Correlation analysis will be conducted to examine if and how frequency and quality of parent-teen communication are correlated; 2) Longitudinal data analyses using mixed-effect models will be performed to further ascertain if the parent training enhances parent-teen communication over time with a focus on how these measures change over time in Group 3; 3) We will conduct further analysis on risky driving events and unsafe driving behaviors using the Quasi-Poisson analysis by including the measures of frequency and quality of parent-teen communication as three additional covariates to evaluate the effects of parent-teen communication, adjusting for group differences.

For the secondary outcome of recidivism, a Cox Proportional Hazards Model will be established to ascertain whether and how much the Device Feedback and/or Device Feedback plus Parent Training intervention reduce the hazard of teen recidivism, adjusting for the potential covariates described above. In addition, the measures of risky driving events and unsafe driving behaviors will be specifically included in the Cox Proportional Hazards Models to examine how risky driving events and unsafe driving behaviors increase the hazards of recidivism, adjusting for potential covariates.

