## 6.0 Procedures Involved\*

### 6.1 Describe and explain the study design.

This study is a randomized controlled trial (RCT) with one control and two intervention groups. Participants will include 240 dyads (80 per group), comprised of one teen driver (ages 16 or 17) who has committed a moving violation (e.g., speeding, failure to obey traffic signal) during the recruitment period and the parent/legal guardian ('parent') who is most involved with the teen's driving. According to Ohio law, when a teen driver under 18 years is cited by law enforcement for a traffic violation, the teen must appear in Juvenile Traffic Court within 2 weeks of the citation accompanied by a parent to confess or deny committing the traffic violation, providing our team with a good opportunity to recruit and enroll participants. After completing informed consent/assent and the baseline assessment, enrolled dyads will be randomly assigned into 1 of 3 groups using a stratified block randomization.

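### Allocation is by stratified blocks, but no analysis in section 17.1 is said to include the strata; if the strata predict risky driving, the one-way ANOVA is conservative and loses some power

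*Combined protocol and SAP*

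**What the plan says.** Section 6.1 of the combined protocol and SAP says that "enrolled dyads will be randomly assigned into 1 of 3 groups using a stratified block randomization". It does not name the stratification factors, the number of strata or the block size, and no other section does.

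Section 17.1 gives two analyses of risky driving events, the outcome on which the trial is sized. The first is "To compare the differences among the 3 groups, one-way ANOVAs will be used". The second is a quasi-Poisson model with two group indicators, "to determine risk ratios of risky driving events among the 3 groups, adjusting for the other potential covariates". Later analyses in 17.1 refer to "adjusting for the potential covariates described above", but no list of covariates comes before those words. The section does not say which of the two analyses is the primary test.

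The sample-size paragraph uses the first analysis. It claims that "this study will have 0.80 or higher power to detect that Group 2 will have fewer risky driving events than Group 1", makes the same claim for Group 3 against Group 2, and bases both claims on 74 evaluable dyads in each group. The method is given as "using a one-way ANOVA and adjusting for two-sided multiple comparisons".

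**The concern.** Stratified blocks balance the three groups within each stratum, so differences between strata largely drop out of the group contrasts. A one-way ANOVA does not use this. It leaves the between-stratum variation in its error term and treats the data as if allocation had been unrestricted. When the strata are prognostic, the reported standard error exceeds the true sampling variability of the contrast.

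Precision is at stake. Intervals would be wider than the design warrants, the test would reject less often than its nominal level under the null, and power already bought by the stratification would go unused. The trial also has to separate Group 3 from Group 2, an incremental comparison where avoidable loss of precision matters. The quasi-Poisson model does not settle the question, because its covariates are unlisted and nothing shows whether the strata are among them.

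**Working it through.** **The plan's own figures.**
- Over-dispersion: 32.7² / 43 = 24.87, which agrees with the plan's 24.9 and its "Quasi-Poisson distribution with an over-dispersion factor of 25".
- Attrition: 1 − 74/80 = 7.5%, consistent with the stated loss of less than 10%.
- Power of 0.80: not reproducible, because section 17.1 gives no effect size, alpha or multiplicity method. It can be solved backwards. With SD 32.7 and 74 per group, the standard error of a difference is 32.7 × √(2/74) = 5.38. The difference detectable with 80% power is 5.38 × (z + 0.842). That is 15.1 at two-sided 0.05 (z = 1.960), 16.6 at 0.025 (z = 2.241, two Bonferroni comparisons) and 17.4 at 0.0167 (z = 2.394, three). These are about 35% to 40% of the pilot mean of 43.

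**Cost of omitting the strata.** Let R² be the share of outcome variance explained by the strata. It is not in the documents, so it is varied. Assume a normal-theory contrast, near-complete balance within strata, and a true difference for which the ANOVA's nominal power is 80%. The true variance of the contrast is then (1 − R²) times what the ANOVA assumes. With s = √(1 − R²), at two-sided 5%:
- ratio of ANOVA to true standard error = 1/s
- false-positive rate = 2 × [1 − Φ(1.96/s)]
- power without strata = Φ(0.84/s)
- power with strata = Φ(2.80/s − 1.96)

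| R² | SE ratio | False-positive rate | Power without strata | Power with strata | Gain (points) |
|---|---|---|---|---|---|
| 0 | 1.00 | 5.0% | 80.0% | 80.0% | 0 |
| 0.05 | 1.03 | 4.4% | 80.6% | 82.0% | 1.4 |
| 0.10 | 1.05 | 3.9% | 81.2% | 84.0% | 2.7 |
| 0.20 | 1.12 | 2.8% | 82.7% | 87.9% | 5.3 |

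(Gains are taken from unrounded values.)

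The plan adjusts for multiple comparisons, so the check was repeated at two-sided 0.025, with z = 2.241 in place of 1.96. Power with strata becomes 82.2%, 84.3% and 88.6% at R² of 0.05, 0.10 and 0.20. Power without strata is unchanged, because Φ(0.84/s) does not depend on z. The gains are 1.6, 3.1 and 5.9 points, so the picture is much the same.

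**Simulation under the null.** Settings: 240 dyads, SD 32.7, normal outcome, 4,000 runs per setting; four strata and blocks of six were assumed.

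| R² | Mean ANOVA SE | True SD of contrast | ANOVA false positives | Stratum-adjusted false positives |
|---|---|---|---|---|
| 0 | 5.16 | 5.19 | 5.7% | 5.6% |
| 0.05 | 5.17 | 5.08 | 4.4% | 5.0% |
| 0.10 | 5.17 | 4.82 | 3.9% | 5.1% |
| 0.20 | 5.18 | 4.64 | 2.8% | 5.2% |

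The Monte Carlo standard error at 5% is √(0.05 × 0.95/4000) = 0.3 points. With non-prognostic strata the ANOVA standard error matches the truth. As R² rises, the ANOVA becomes conservative and the adjusted test stays close to 5%.

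**The case against.** The strongest reply has four parts.

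1. **The strata are unnamed, so nothing shows that they predict driving events.** This stands. A reader might infer that the ANOVA standard errors are too wide outright, but that holds only if R² is above zero. A gain of 5 points needs R² of about 0.2, and nothing in the documents suggests the strata explain that much.

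2. **The ANOVA may not be the decisive analysis.** Section 17.1 gives the quasi-Poisson model the task of modelling the intervention effect, and its covariates could include the strata. This stands in part. An unlisted set does not show that the strata are excluded, but neither does it show that they are included, and the ANOVA is the test behind the sample size.

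3. **No promise is broken.** This also stands. A reader might infer that the trial falls short of its stated power or that its error rate is unsound. In every row of the analytic table the unadjusted power is at least 80% and the false-positive rate is at most 5%. A positive ANOVA result would not be undermined.

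4. **The result belongs to linear models.** It should not be carried over to the Cox model for recidivism. Hazard ratios are non-collapsible: omitting a prognostic stratum attenuates the estimated ratio, and including it changes what is estimated and can increase the standard error. The objection is right that the Cox intervals cannot be called too wide on this ground.

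**Conclusion.** The point holds as a conditional loss of efficiency. The design stratifies, the ANOVA used for sizing and for the three-group comparison omits the strata, and no other model is documented as including them. For an assumed R² of 0.05 to 0.20 the cost is about 1 to 5 points of power for a single contrast at two-sided 5%; at R² of 0 it is nil. The direction is conservative throughout.

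The figures assume a normal outcome and near-complete within-stratum balance. Many incomplete blocks would reduce the effect, and the over-dispersed counts in this trial may behave somewhat differently. The change is worth making because it is cheap and fixes the model in advance, not because the present plan would give a false result.

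**What to change.** In section 17.1:

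- Name the stratification factors. The remaining changes cannot be written until this is done.
- Replace the one-way ANOVA by a model with group and randomisation stratum as fixed effects, and take the contrasts 2 v 1, 3 v 1 and 3 v 2 from the stratum-adjusted model. Keep the unadjusted ANOVA as a descriptive supplement.
- Enter the same stratum terms in the quasi-Poisson models and the ANCOVAs, list the other covariates, and say which analysis of risky driving events is primary.
- In the Cox model, stratify by or adjust for the same factors, for consistency with the design.

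The cost is wording, one or a few terms in the code, and probably a few degrees of freedom out of about 220 (3 × 74 = 222 evaluable dyads); the exact number depends on how many strata there are. Stratum membership has to be known at allocation, so no new data collection and no change to enrolment should be needed.

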### 2.2 State the hypotheses to be tested.

Aim 1: Hypotheses: The two intervention groups will demonstrate significant reductions in risky driving events (hard braking, sudden acceleration, speeding) and unsafe driving behaviors (speeding, no seatbelt use, distracted driving) per 1,000 miles driven when compared to the control group; The Driving-Feedback plus Parent Communication Training group will have fewer risky driving events and unsafe driving behaviors than the Driving Feedback Only group.

Aim 2: Hypothesis: The Driving-Feedback plus Parent Communication Training group will engage in more frequent and higher quality parent-teen communications on safe-driving topics than the other two groups.

Aim 3: Hypothesis: The two intervention groups will demonstrate significant reductions in recidivism (subsequent traffic violations) when compared to the Control group; The

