**6.4 What data will be collected during the study and how that data will be obtained.**

1. Risky driving events (hard braking, sudden acceleration, speeding): will be collected among teens in all three groups using the Azūga™ in-vehicle device. The number and type of driving event, including hard braking ( $\leq -0.45$  g-force) sudden acceleration ( $> 0.35$  g-force), and speeding ( $>10$  miles over the posted speed limit), and speed  $>75$  mph will be automatically coded and counted in the system. The rates will be computed by dividing events by miles driven then multiplying by 1,000.
2. Unsafe driving behaviors: Using the Azūga™ in-vehicle device and smartphone app, we will collect data on teen's unsafe driving behaviors (e.g., speeding, no seatbelt use). The duration (e.g., miles driven) and type of driving behaviors, including speeding ( $>10$  miles over the posted speed limit), will be automatically coded and counted in the system. The proportions will be calculated by dividing by miles driven then multiplying by 1,000 (e.g., proportion of 1,000 miles in which speeding). In addition, surveys will collect self-reported distracted driving (e.g., calls made and received, texts sent and viewed while driving, searches for a webpage/app) and seatbelt use (since not all vehicle models are available via Azūga™ in-vehicle device).

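### The planned correlation between risky driving events and unsafe driving behaviors does not exclude the device-recorded speeding that both outcomes contain, so a nonzero result cannot by itself show that the distinct behaviors are related

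*Combined protocol and SAP*

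**What the plan says.** The Aim 1 hypotheses in Section 2.2 define the two outcomes with speeding in each: "risky driving events (hard braking, sudden acceleration, speeding) and unsafe driving behaviors (speeding, no seatbelt use, distracted driving".

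Section 6.4 says how each is measured.

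- Item 1: "Risky driving events (hard braking, sudden acceleration, speeding): will be collected among teens in all three groups using the Azūga™ in-vehicle device". Speeding means more than 10 miles over the posted limit. For the scale, "The rates will be computed by dividing events by miles driven then multiplying by 1,000".
- Item 2: "Using the Azūga™ in-vehicle device and smartphone app, we will collect data on teen's unsafe driving behaviors (e.g., speeding, no seatbelt use". The speeding threshold is the same, but the scale is not a count: "The duration (e.g., miles driven) and type of driving behaviors, including speeding". This quantity is also divided by miles driven and multiplied by 1,000. Distracted driving is self-reported by survey, as is seatbelt use, because the device cannot record it in every vehicle model.

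Section 17.1 states for risky events that "the overall rate and rate for each type of event per 1,000 miles driven will be calculated for each teen at" the 6-month follow-up. It lists the components of the second outcome again: "For the primary outcome of unsafe driving behaviors (speeding, distracted driving, no seatbelt use". It then adds the secondary analysis of correlation coefficients "to ascertain if and how the risky driving events and unsafe driving behaviors are correlated and whether the correlations are different between the study groups", with adjustment for potential covariates. Speeding is not named as one of those covariates. The section does not say which variables enter the correlation, and it gives no type of coefficient, reference value or alpha.

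**The concern.** The analysis asks whether two kinds of driving go together. A coefficient answers that cleanly only if zero is what unrelated behaviors would produce. Here, a teen with more speeding events will usually also have more speeding miles. Two measures that each contain one of these will tend to correlate even if braking and acceleration have nothing to do with seatbelt use or distraction. If the correlations are instead taken by component, nothing rules out pairing speeding events with speeding miles, which measures agreement between two records of one behavior.

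The stake is interpretation. A report could say that risky events and unsafe behaviors are associated when the figure partly or wholly reflects speeding on both sides. The comparison between groups could be misread in the same way if the intervention changes how much speeding contributes.

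**Working it through.** The documents give no figure for this analysis, so there is none to reproduce.

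**Inputs from Section 17.1.** 74 evaluable teens per group, so 3 × 74 = 222 in total. Pilot mean 43 and SD 32.7, with 32.7²/43 = 24.9, which matches the stated over-dispersion of about 25.

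**Assumed inputs.** Two-sided alpha of 0.05; the share f of each measure's variance that comes from speeding; the correlation ρ between speeding-event rate and speeding-mile rate. The documents give none of these, so f and ρ are shown as ranges.

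**Step 1: correlation from overlap alone.** Suppose overall measures are correlated and all components other than speeding are independent. Then the built-in correlation is ρ × √(f₁ × f₂). With f₁ = f₂ = 1/3 and ρ = 0.8, it is 0.8 × 1/3 = 0.267.

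**Step 2: probability of rejecting zero.** By Fisher's z, the standardized shift is d = atanh(built-in correlation) × √(n − 3), and the rejection probability is Φ(d − 1.96) + Φ(−d − 1.96). For 0.267, atanh = 0.273.

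- n = 74: d = 0.273 × √71 = 2.30, rejection 63%.
- n = 222: d = 0.273 × √219 = 4.04, rejection 98%.

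| Share f (both sides) | ρ | Built-in correlation | Rejection, n = 74 | Rejection, n = 222 |
|---|---|---|---|---|
| 0.05 | 0.5 | 0.025 | 5.5% | 6.6% |
| 0.10 | 0.8 | 0.080 | 10.4% | 22.0% |
| 0.20 | 0.5 | 0.100 | 13.5% | 31.8% |
| 0.20 | 0.8 | 0.160 | 27.5% | 66.6% |
| 1/3 | 0.5 | 0.167 | 29.4% | 70.2% |
| 1/3 | 0.8 | 0.267 | 63.4% | 98.1% |
| 1/3 | 1.0 | 0.333 | 83.2% | 99.9% |
| 0.50 | 0.8 | 0.400 | 94.6% | over 99% |

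**Step 3: check with skewed counts.** Five independent negative-binomial components were simulated, with equal means and a variance-to-mean ratio of 25 (4,000 runs per setting, Pearson test).

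- Speeding identical on both sides: mean correlation 0.33, rejection 79% at n = 74 and 99.7% at n = 222.
- Miles per speeding event varying widely (log-SD 1): mean correlation about 0.25, rejection 54% and 93%.
- Speeding left out of both sides: mean correlation about 0, rejection 4.7% and 6.0%.

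The simulation did not model the miles-driven denominator, so it says nothing about correlation from that source.

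**Step 4: comparison between two groups.** Suppose feedback halves the SD of speeding in one group and leaves the variance of everything else unchanged. With speeding variance 1 and other variance 2, the share falls from 1/3 to 0.25/2.25 = 1/9. At ρ = 0.8 the built-in correlation falls from 0.267 to 0.8/9 = 0.089. The difference in z is 0.273 − 0.089 = 0.184 and its standard error is √(2/71) = 0.168, a ratio of 1.10. A nominal 5% test of equal correlations then rejects about 20% of the time. If the other variances shrink in the same proportion, the share stays at 1/3. With ρ also the same in both groups, the overlap creates no difference.

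**The case against.** The strongest reply is that the plan does not specify the analysis being criticized. Section 17.1 speaks of coefficients in the plural. It calculates event-type rates as well as an overall rate, and it defines no summed total for unsafe behaviors, whose components are in different units. Component correlations fit the wording as it stands. No test against zero is written, and a purely descriptive reading is possible. Correlating the two outcomes as the protocol defines them is also a legitimate descriptive question. All of this stands. It does not remove the need for a rule, because neither the overall reading nor the component reading keeps speeding off both sides.

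A reader might infer more than the documents support:

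- *That any significant correlation would be produced by the overlap and not by a real relation.* The table runs from near the nominal 5% to over 99%, and the inputs that decide between these are not given. A real relation may exist as well.
- *That independence is impossible by construction.* The shared item is a count on one side and miles on the other, so it is overlapping information and not an identical term. Section 6.4 also codes speed above 75 mph among the events, with no counterpart on the other side. Relations among the other components could add to the shift or offset it.
- *That feedback would make the correlations differ between groups.* This needs speeding's share of variance, or the event-mile relation, to differ by group. Section 2.2 hypothesizes reductions in the other behaviors too, so the share need not change.

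**Conclusion.** The concern holds in a limited form. Speeding from one device at one threshold belongs to both outcomes, and the plan for the secondary correlation does not exclude it. Zero is therefore not a clean reference value for overall measures, or for speeding events against speeding miles. A nonzero coefficient cannot by itself show that braking and acceleration are related to seatbelt use or distraction.

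How much this matters is not known from the documents. The central example, 98% at N = 222, rests on an assumed share of 1/3, an event-mile correlation of 0.8, independence of all other components and an assumed test of zero. At a share of 0.05 the effect nearly vanishes. The between-group example of about 20% is conditional in the same way.

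The importance is low. No aim, hypothesis, sample-size statement or primary group comparison depends on this analysis.

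**What to change.** In Section 17.1, state that the correlations and their comparison between groups use non-overlapping components: hard braking plus sudden acceleration per 1,000 miles against each unsafe behavior separately (miles speeding, seatbelt non-use, distracted driving). Report any correlation of speeding events with speeding miles, or of overall measures that contain both, as descriptive only and labelled as sharing speeding. Note that quantities divided by miles driven still share that denominator, which this change does not remove.

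The cost is a few lines of wording. The event-type rates are already planned, so no new data are needed. The downside is three coefficients in place of one, overall and by group, which should be read with that number in mind.
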